6.6 Primary study parameter(s)

Statistical analysis will examine agreement between different measures of substance use (sensitivity, specificity and AUC value) to evaluate the level of classification accuracy for each items or candidate combination of items.

This study will not include follow up assessments. We expect a number of patients who don't want the assessment at all or don't want to sign informed consent. The extent of missing data will be analyzed and explore differences in missing data by age, gender, and diagnosis.

On objective 1 the primary study parameters are TAPS and MATE outcomes. The total TAPS-score is used as

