3. STUDY DESIGN

This is a descriptive study based on routinely collected data. The FACT teams that participate in the study work according to a care program in which screening and assessment are part of the standard care. This implies that since 2016, screening has been carried out at the start of treatment for: PTSD, a mild intellectual disability, addiction problems. The current screening for addiction problems is too limited and lacks a follow-up step in the form of structured assessment. In addition, at the start of treatment and annually in preparation of the treatment plan, the level of complaints is assessed by the care provider involved and the phase of recovery and the patient's quality of life are assessed. We want to use this data from patients in whom there is no suspicion of mild intellectual disability in anonymised form. In the research into the validity of the TAPS, we want to measure whether there is a relationship between the existence of problem substance use and a poorer treatment outcome (less decrease in complaints), and a reduced quality of life.

The TAPS has already been included as a replacement for the previously used screener for addiction problems by the various substantive advisory bodies that deal with the content and improvement of the care of the GGZ Oost Brabant.

In order to investigate the concurrent validity of the TAPS, a group of at least 40 patients will be asked permission to administer some parts of the MATE in addition to the TAPS.

The TAPS is too difficult for patients with intellectual disabilities. We therefore made adjustments to the translated TAPS (see below). The adjusted version for patients with ID is called the TAPS-ID. The validity of the TAPS-ID is examined by the comparison of the TAPS-ID and the SumID-Q (an instrument specially developed to map addiction problems in patients with MID). This will be carried out in a special department within secondary healthcare for patients with a combination of a severe mental disorder and intellectual disability (LVB-P) and in a healthcare setting for people with intellectual disabilities with minimal or light mental disorders (ORO). The SumID-Q is part of standard care for both departments. Trained employees who administer the SumID-Q also take the TAPS-ID.

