4.4 Sample size calculation

The number of new registrations for FACT teams is between 30 and 40 per year. With a minimum of three participating FACT teams, there are approximately 100 new patients per year. In the 2.5 years of the planned data collection, there will be 250 new patients. Based on the information that approximately 40% of FACT patients function at the level of mild intellectual disability, we can include at least 150 patients. A very substantial part could refuse to participate in order to obtain the required 40 patients for the validity study.

The SumID-Q is administered at least 20 times a year within the various parts of the LVB-P department (ambulatory, part-time, clinic). Most administrations take place at the clinic, where SumID-Q administration is standard of care at the start of clinical admission. ORO also uses the SumID-Q more than ten times a year. The required 40 patients seems achievable within the period of data collection.

For both groups, we stop data collection at 100 participating patients.

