5.3 Study procedures

Objective 1:

The validation study of the TAPS was incorporated in a broader comprehensive screening and assessment procedure that is standard care in FACT teams in this mental healthcare institute.

All new patients were screened on intellectual disabilities, trauma-related symptoms and substance use problems. Actual psychiatric symptoms, quality of life, phase of recovery and the burden of care for relatives of the patient were also mapped. This screening and assessment consisted of one test, four self-report questionnaires for the patient, one questionnaire for relatives and one questionnaire for the caregiver. The TAPS-tool was used for screening and brief assessment of substance use problems. Only when a patient was incapable of concentrating for more than 15 minutes, when the Dutch language was a problem or when there was almost no cooperation for the FACT treatment at all, the screening and assessment was omitted.

Psychologists or case managers were the assessors. They invite the patient for an appointment to take the test and fill out the questionnaires together at home or at the office. The screening on possible intellectual disabilities was done first. There was no fixed order for the other parts.

For the validation of the TAPS two elements were added to the standard procedure: First, the assessor also took the parts of the MATE necessary to investigate the severity of the addiction (module 1, 4, and Q1; see description of the MATE above). Second, after completing the TAPS and the MATE, but before the scoring of it, the assessor also rated the severity of the substance use problems on a five-point Likert

scale by answering the following question: "I rate the addiction problem of the client as...". Possible answers were: absent, mild, moderate, severe, very severe .

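### Objective 1: the comparison of patients with and without the MATE omits the TAPS result, so it cannot show whether the verified sample differs on the test being validated

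*Combined protocol and SAP*

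**What the plan says.** All references are to the combined protocol and SAP.

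- **The index test is routine.** Section 3: "The TAPS has already been included as a replacement for the previously used screener for addiction problems". Section 5.3: "All new patients were screened on intellectual disabilities, trauma-related symptoms and substance use problems". There are exceptions: "Only when a patient was incapable of concentrating for more than 15 minutes, when the Dutch language was a problem", or almost no cooperation with treatment. Section 6.6 also expects some patients to decline the whole assessment.
- **The reference standard is an addition for consenters.** Section 3: "a group of at least 40 patients will be asked permission to administer some parts of the MATE in addition to the TAPS". Section 5.3: "For the validation of the TAPS two elements were added to the standard procedure", the first being the MATE modules.
- **Numbers.** Section 4.4 expects at least 150 eligible patients, requires 40 and stops at 100. It adds: "A very substantial part could refuse to participate in order to obtain the required 40 patients for the validity study".
- **Analysis.** Section 6.6 plans sensitivity, specificity and AUC, and the Statistical Analysis section sets the cut-off by ROC. For missing data, section 6.6 will "explore differences in missing data by age, gender, and diagnosis". No section compares TAPS results by MATE status or plans an adjustment. The descriptive overview of substances in section 6.7 is not split by participation.
- **Data available.** Section 3, on the routine measurements: "We want to use this data from patients in whom there is no suspicion of mild intellectual disability in anonymised form".

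**The concern.** When everyone has the index test but only some have the reference, accuracy in the verified subset can be distorted by who was verified. The variable that matters most for detecting this is the index test result, and it is the one left out. Verified and unverified patients could match on age, gender and diagnosis and still differ sharply in the proportion who are TAPS-positive.

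A plausible route exists. A patient reluctant to disclose may both give a negative self-reported TAPS and refuse further addiction questions. Refusal is then linked to the TAPS result even among patients with the same true status. Any distortion would reach the reported accuracy of the Dutch TAPS and its recommended cut-off.

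**Working it through.** **1. The plan's own figures (section 4.4).** 100 patients per year × 2.5 years = 250. 250 × (1 − 0.40) = 150 eligible, as stated. The quoted 30 to 40 registrations per team, with three teams, give 225 to 300 new patients and 135 to 180 eligible. With 150 eligible, the verified fraction is 40/150 = 26.7% at the minimum (110 without MATE) and 100/150 = 66.7% at the stopping number (50 without MATE).

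**2. Consent depends on the TAPS result.** The documents give no consent rate by TAPS result, so all rates here are assumptions. Let v+ and v− be the MATE uptake in TAPS-positives and TAPS-negatives.

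- Apparent sensitivity = Se·v+ / (Se·v+ + (1−Se)·v−)
- Apparent specificity = Sp·v− / (Sp·v− + (1−Sp)·v+)

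Neither depends on prevalence. With assumed true Se 0.80 and Sp 0.85:

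| v+ | v− | Apparent sensitivity | Apparent specificity |
|---|---|---|---|
| 0.20 | 0.35 | 0.16/0.23 = 0.696 | 0.2975/0.3275 = 0.908 |
| 0.35 | 0.20 | 0.28/0.32 = 0.875 | 0.17/0.2225 = 0.764 |
| 0.55 | 0.75 | 0.44/0.59 = 0.746 | 0.6375/0.72 = 0.885 |

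At an assumed prevalence of 30%, 150 patients contain 36 true positives, 9 false negatives, 15.75 false positives and 89.25 true negatives. That is 51.75 TAPS-positive and 98.25 TAPS-negative. Row 1 verifies 0.20 × 51.75 + 0.35 × 98.25 = about 45. Row 3 verifies about 102, close to the stopping number.

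As a second illustration, take the alcohol figures quoted in section 5.3 (0.74 and 0.79) as true. An uptake ratio v+/v− of 0.5 gives 0.587 and 0.883; a ratio of 2 gives 0.851 and 0.653. A ratio of 1 gives no bias.

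**3. Consent depends only on true status.** Use the same 150 patients, with uptake of 20% in those with the disorder and 35% in those without. Verified counts are TP 7.2, FN 1.8, FP 5.51 and TN 31.24.

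- Crude sensitivity = 7.2/9 = 0.80 and crude specificity = 31.24/36.75 = 0.85, both unbiased.
- Uptake still differs by TAPS result: 12.71/51.75 = 24.6% against 33.04/98.25 = 33.6%.
- Begg-Greenes takes PPV = 7.2/12.71 = 0.566 and NPV = 31.24/33.04 = 0.946 and applies them to all 150. It returns 0.846 and 0.805, both wrong.
- With the two uptake rates exchanged it returns 0.737 and 0.890.

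Unequal uptake by TAPS result is therefore a warning sign, but it does not identify which mechanism is at work.

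**4. Sampling error.** In row 1 about 10 patients with the disorder are verified (7.2 + 3.15). The exact 95% interval for 7/10 is 0.35 to 0.93, wider than the shift of about 0.10.

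**The case against.** The strongest objection is that nothing in the plan makes the MATE conditional on a TAPS score. Under section 5.3 the study is raised by telephone at least a day ahead, consent is signed at the appointment, and scoring follows completion of both instruments. If refusal follows true substance use, crude sensitivity and specificity are sound and an automatic correction would harm them. This stands, and step 3 of the working confirms it. It does not remove the risk, because reluctance to disclose can link refusal to the TAPS answer within a given true status.

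Other limits also stand:

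- The remark on refusal in section 4.4 describes headroom; it does not predict a refusal rate. Because collection stops at 100, not everyone without a MATE need be a refuser.
- Patients who decline everything, or fall under the section 5.3 exceptions, have no TAPS result. For them only background variables can be compared.
- Any adjusted estimate would rest on very few false negatives if only about 40 patients are verified.
- The consent described in section 5.3 covers the TAPS answers, so use of refusers' TAPS results needs confirmation. Against this, section 3 already plans anonymised use of routine data, and the section 6.6 comparison already needs data on non-participants.

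**Conclusion.** The point holds for objective 1, as an inexpensive improvement. The planned comparison cannot show whether the verified sample represents the screened patients on the TAPS, although the data to show it are largely collected already. The possible size is material: about 0.10 in sensitivity and 0.06 in specificity in the first scenario, and 0.08 and 0.09 in the opposite direction in the second. Those figures rest on assumed accuracy and assumed consent rates, and on consent depending on the TAPS result given true status.

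A reader might infer more, and the documents do not support it:

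- **That the accuracy estimates are biased.** No section gives uptake by TAPS result or ties the MATE to it. The bias is a risk of unknown direction.
- **That a Begg-Greenes correction should replace the crude values whenever uptake differs.** It assumes the MATE is missing at random given the TAPS, and it misleads if refusal depends on true status.
- **That counts of TAPS-positive and TAPS-negative unverified patients are enough.** Section 6.6 covers each item and candidate combination, and a ROC cut-off is planned, so the score distribution is needed. A positive TAPS-1 on any section includes any past-year tobacco use and is not the index result for a given substance.
- **That the same applies to objective 2.** There the SumID-Q is standard care and the TAPS-ID is the consented addition (section 5.3).

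**What to change.** In section 6.6, for objective 1:

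1. Add the TAPS result, by substance category and score and at the thresholds analysed, to the comparison of patients with and without the MATE, using the anonymised routine data described in section 3. Report separately the number with no TAPS at all.
2. Keep the crude sensitivity, specificity and AUC as primary.
3. If MATE uptake differs by TAPS result, add a Begg-Greenes or inverse-probability-weighted estimate, labelled as a sensitivity analysis. State that it assumes the MATE is missing at random given the TAPS, and that it would mislead if refusal depends on true status.
4. Confirm that the basis for using anonymised routine data covers the TAPS results of patients who refused the MATE. If it does not, state as a limitation that the verified sample could not be compared with the screened patients on the TAPS.

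The cost is SAP wording, a few lines of analysis, a MATE yes/no marker in the anonymised file, and the confirmation in item 4. No extra patients, visits or questions are needed.

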6.7 Secondary study parameter(s)

The analysis of size and content of addiction problems will be done by an overview of descriptive statistics of the whole patient population, sorted by different substances being used.

For objective 1 the correlation with quality of life (MANSA) and amount of mental complains and social functioning (HoNOS) is also calculated for the divergent validity.

6.8 Other study parameters

6.9 Interim analysis (if applicable)

Na.

7. ETHICAL CONSIDERATIONS

7.1 Regulation statement

This study will be conducted in compliance with the appropriate protocol, current Good Clinical Practice (GCP), the principles of the Declaration of Helsinki 2008 and all other applicable regulatory requirements.

7.2 Recruitment and consent

See above (procedure)

7.3 Objection by minors or incapacitated subjects (if applicable)

Not applicable

7.4 Benefits and risks assessment, group relatedness

<Please give a justification of the proposed study.>

7.5 Compensation for injury

The sponsor/investigator has a liability insurance which is in accordance with article 7 of the WMO.

The sponsor (also) has an insurance which is in accordance with the legal requirements in the Netherlands (Article 7 WMO). This insurance provides cover for damage to research subjects through injury or death caused by the study.

The insurance applies to the damage that becomes apparent during the study or within 4 years after the end of the study.

7.6 Incentives (if applicable)

N.a.

8. ADMINISTRATIVE ASPECTS, MONITORING AND PUBLICATION

8.1 Handling and storage of data and documents

The anonymous data will be saved on an SPSS-file which is placed in a file where only the investigators and research assistant from the specific research area of FACT patients within the GGZ Oost Brabant have access to.

8.2 Monitoring and Quality Assurance

This research is part of a PhD study. The progress of this research is monitored every 6 weeks by professors involved in the PhD project. In addition to that, the progress is yearly monitored by the commission for scientific research (CWO) at the GGZ Oost Brabant.

The main researcher ([name]) yearly gives the CWO an update and progression will be tested.

8.3 Amendments

All amendments will be notified to the ECSW that gave a favourable opinion.

8.4 Annual progress report

The sponsor/investigator will submit a summary of the progress of the trial to the CWO of GGZ Oost Brabant once a year. Information will be provided on the date of inclusion of the first subject, numbers of subjects included and numbers of subjects that have completed the trial, serious adverse events/ serious adverse reactions, other problems, and amendments.

8.5 Temporary halt and (prematurely) end of study report

The investigator/sponsor will notify the CWO and ECSW of the end of the study within a period of 8 weeks. The end of the study is defined as the last patient's last visit.

The sponsor will notify the CWO and ECSW immediately of a temporary halt of the study, including the reason of such an action.

In case the study is ended prematurely, the sponsor will notify the CWO and ECSW within 15 days, including the reasons for the premature termination.

Within one year after the end of the study, the investigator/sponsor will submit a final study report with the results of the study, including any publications/abstracts of the study,

to the CWO and ECSW.

8.6 Public disclosure and publication policy

The outcome data of this two objectives are sent to a scientific journal.

9. STRUCTURED RISK ANALYSIS

N.a. (No product of risk is used)

